Evaluation of Wear Experience with Water Surface Toric Contact lenses
on long lens-wear days

NCT 04844281

Evaluation of Wear Experience with PRECISION1® Toric Contact lenses

on long lens-wear days

[name], OD MS

The Ohio State University College of Optometry
Innovation in Vision and Eye care Research Group - iVERG

Purpose

The purpose of this study is to explore the performance of PRECISION1® Toric lenses on long days of lens wear.

Study Overview

This open-label study is of current soft contact lens wearers who wear their contact lenses for longer than a typical workday. Participants who regularly wear contact lenses for long days will be fit into PRECISION1® Toric contact lenses. Participants will be assessed after 1-2 weeks of wear with a follow up visit (Visit 2) to ensure a successful lens fit. Refitting will occur if necessary. After final completion of Visit 2, the five survey days will be determined. On 5 days between Visit 2 and Visit 3, the participant will respond to a survey sent to their smart phone to report the time they insert their lenses each morning. Each evening, the participant will be sent a survey for immediate response about their current comfort and vision with lens wear. The surveys will be sent at 10, 12, 14 and 16 hours of lens wear. Participants will return for a final follow-up visit including a VAS survey and the CLDEQ8 survey of their lens wear experience.

Background

Soft daily wear contact lenses are used by an estimated 40.9 million adults in the United States.¹ Contact lenses which are worn for daily wear are considered minimal risk by the FDA, and risks to wearers are minimized by proper lens care and hygiene. Daily disposable contact lenses do not require daily cleaning and overnight storage, which lessens the required amount of time to care for contact lenses. In addition, daily disposable contact lenses are associated with less lens deposits, which decreases associated comfort issues in lens wearers, including decreasing the risk of triggering Giant papillary conjunctivitis (GPC) and/or ocular allergic responses in patients.² Additionally, daily disposable contact lens wearers are not likely to expose their lenses to water and tend to have better lens hygiene since these lenses do not require daily cleaning. This is reflected in a study which found less superficial punctate staining and symptoms of dryness when comparing daily disposable contact lens wear with planned replacement lenses.³ The subjects in this study will be fit into PRECISION1 toric daily disposable contact lenses, which are less likely to be associated with the already minimal risks of daily contact lens wear. Because of these benefits of

daily disposable lenses, and the accompanying improvement in comfort, it is likely that these lenses will provide long lasting comfort and vision throughout the day. As many people wish to wear their contact lenses to work and then throughout the evening, it is of interest to know how a lens performs over the course of a day into evening.

Key Endpoints:

- Subjective assessment of comfort and vision at time points of extended contact lens wear (Scale of 1 -10) at evening time points on 5 days.
- Visual Analog Scale survey of lens wear symptoms (comfort, dryness, vision) at study end.

Study Time Points:

Visit 1 will be conducted to consent the subject and determine eligibility. Consenting will be conducted via phone call and REDCap and will occur before the subject arrives on site if possible. After consenting, the visit will begin with visual acuity and an evaluation of the subject's ocular health will occur to determine eligibility including positively responding to the question, "Do you currently wear contact lenses over a long day?" This will ensure that subjects are able and willing to participate in the study since long contact lens wear will be needed. Subjects will be asked their normal morning time for inserting lenses and evening time for lens removal. Eligible subjects can be habitual wearers of soft toric contact lenses and will be fit into PRECISION1®Toric Contact Lenses at this visit and will have a fit assessment and over-refraction completed in order to obtain the best fit and vision. Surveys of impressions of lenses will be completed. For any participant who is an existing PRECISION1® Toric wearer, the lenses will be evaluated and the prescription will be refined if necessary. Any existing PRECISION1® Toric wearer who does not require any changes in prescription at Visit 1 can immediately advance to Visit 2. Otherwise, all participants deemed eligible will be dispensed study lenses and Visit 2 will be scheduled.

Visit 2: Precision 1 Toric follow-up visit will occur approximately 1 week (± 5 days) following Visit 1. Visual acuity and contact lenses fit assessment and over-refraction will be completed. If changes to the lens are necessary, those changes will be made and an additional follow up visit will be scheduled. Subjects will be asked their normal morning time for inserting lenses and evening time for lens removal. Subjects who are new to PRECISION1® Contact Lenses will be dispensed additional lenses to wear until Visit 3.

Five evening survey days: On the morning of each survey study day, the participant will respond to a survey with the time when they inserted their contact lenses that day.. Participants will later be deployed a brief survey at 10, 12, 14 and 16 hours of lens wear that day via REDCap. The surveys will be deployed electronically on 5 days between Visit 2 and Visit 3 that are determined at the time of Visit 2. Every attempt will be made to complete the surveys on business days if possible.

Final visit: The contact lens follow up visit will occur approximately 1 week (± 5 days) following the follow up visit. Subjects will have visual acuity, an assessment of ocular health. Subjects will then complete surveys about their lens wear experience.

Evening Surveys will include 1-10 forced choice grading of comfort and vision.

End of study surveys will include a lens experience survey, the CLDEQ-8 survey, and VAS scales assessing:

Overall Quality of vision
End of Day Quality of vision
Overall comfort
End of Day comfort
Overall dryness
End of Day dryness

Recruitment

Potential subjects may see posters placed on bulletin boards at The Ohio State University or local eye care offices, emails to students, faculty and staff at OSU, online or paper ads, or signs on the OSU buses. A search of the electronic medical records of The Ohio State College of Optometry may be done to identify possible subjects who then may be contacted by email or phone with information about the study. Word of mouth referrals by study team members to OSU employees and friends may occur. Emails to alumni of the OSU College of Optometry may be sent for local doctors to notify eligible potential subjects about the study.

Inclusion criteria:

- Ages 18-40
- Subjects must be current soft toric contact lens wearers with longs days of lens wear within the parameters of P1 lenses available.
- Subjects must have 20/25 or better distance visual acuity with current lenses.
- Subjects should have had an eye exam in the past two years (self report).
- Good general health (defined by medication use that has not changed within the last month and the absence of medical conditions or treatments that are deemed confounding to the data as determined by the PI).
- Ability to give informed consent.
- Subjects must have a working smart phone or device and be willing to receive and respond to texts and or emails.
- Willing to spend time for the study. Subjects will be required to attend three study visits (with a possible fourth visit if needed), wear contact lenses on days between study visits, and must respond to communications on a smart phone or other electronic device on 5 weekdays between visits 2 and 3.
- Either gender.
- Any racial or ethnic origin.

Exclusion criteria:

- No current ocular inflammation or infection as assessed by the study investigator.
- Females who are currently pregnant or lactating or plan to become pregnant during the course of the study.

Consent and Confidentiality

A team member trained in the consent process will provide the consent document for the potential subject to read and will review the procedures with reference to the consent form. The individual is then provided with time to read the consent form and offered the opportunity to ask questions. The participant is explicitly told that they may stop participation at any time. All subjects will have the capacity to give informed consent. If there is any doubt as to the subject's ability to consent to the study, the subject will be excluded from the study. If the subject agrees to take part in the screening or measurement, he or she will sign and date the most recent IRB-stamped consent as will the team member. The subject will be provided with a copy of the consent form.

The investigator team is trained in privacy issues and will be reminded of the importance of patient privacy prior to study initiation. Potential study participants will contact us after seeing advertisements, emails or hearing about the study by word of mouth, giving them the choice of whether or not they wish to participate in a study for people with dry eyes. Privacy is protected by limiting information related to study recruitment only, and no other personal or medical information that should be private to the patients. The PHI needed is only for the purposes of this study. It is highly unlikely, indeed extremely remote that the dry eye symptoms or signs are related to private or personal information that should or would be preferred to be kept confidential to the patients. Risk factors for dry eye rarely relate to matters or conditions that would be personal to the patient such as personal relationships, behaviors or diseases that one prefers to keep private and confidential.

Statistical Analysis and Power Calculation

This small sample size was chosen for convenience as this study as enrollment for evening participation may be difficult.

Data Management and Security

During the active stages of the study (recruitment to last measurement visit), all paperwork (consents, questionnaires and data forms) for each subject will reside in a subject folder for easy access throughout the study. The folders will reside in the limited-access research area, in a locked file drawer or cupboard. At the completion of the study or disenrollment of a subject the paperwork in the subject's folders will be reorganized into a regulatory binder (consents, W-9s) and a data binder (questionnaire and data forms) and will reside in an office in the limited-access research area. When the data analysis is completed and the study is considered complete, the binders will be stored in the secure Department or Office Clinical Research Area. Paperwork (questionnaire and data forms) for individuals who participate in the baseline visit but are not eligible to continue the study will be stored in the study regulatory binder in an office in

the limited-access research area. An electronic file of potential subjects and a file of enrolled subjects with their contact information, as well as electronic files of collected data with the subject number, will reside on a limited-access shared drive with firewall and password protection and is restricted to individuals in the research team. Any electronic data files that contain PHI will be destroyed at the conclusion of the study.

Risks to Subjects and Mitigation

Although rare, a subject could experience eye pain, changes in vision, continued redness or irritation of the eye when inserting or learning to insert a contact lens. More likely transient blurring of vision (less than one minute) or mild, transient (less than a minute) stinging may occur.

Adverse Events

All adverse events will be documented and reported under the guidelines of The Ohio State University Event Reporting guidelines, with any serious, unanticipated and related events being reported to the IRB, by the PI, within 10 days. Adverse Events information will be summarized in the annual report to the IRB at the end of the study. Adverse events will be assessed and determined by [name].

Subject Dismissal

Subjects who, after study team member coaching, are not able to provide analyzable data may be dismissed from the study. Analyzable data is, for example, that which is obtained for the entire measurement interval and provides a readable eye image. Data may not be analyzable if patient isn't able to stand or move freely to utilize the equipment, to name just two causes issues. These issues are usually revealed at the screening assessment visit. Subjects who cannot provide analyzable data will be dismissed for the study. Subjects who do not keep scheduled visits within the required time frame will be dismissed from the study. Study team members will make reasonable efforts to accommodate subjects' schedules.

Protocol Violations, Discontinuation

In the event that a member of the study team or a representative of sponsor becomes aware of a major protocol violation, the IRB shall be notified within 10 working days.

References

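### Survey-day comfort and vision are rated only at 10, 12, 14 and 16 h and nothing is recorded at lens removal, so the late ratings describe only days still in wear

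*Protocol*

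**What the plan says.** The first key endpoint is "Subjective assessment of comfort and vision at time points of extended contact lens wear (Scale of 1 -10) at evening time points on 5 days" (Protocol, Key Endpoints). The Study Overview fixes when the ratings are taken, "The surveys will be sent at 10, 12, 14 and 16 hours of lens wear", and the paragraph on the five evening survey days under Study Time Points repeats the same four hours.

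Each evening, "the participant will be sent a survey for immediate response about their current comfort and vision with lens wear" (Study Overview). On content, the protocol says "Evening Surveys will include 1-10 forced choice grading of comfort and vision" (Study Time Points, after the final visit).

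Two further items concern wear times. On each survey morning, "the participant will respond to a survey with the time when they inserted their contact lenses that day". At Visits 1 and 2, "Subjects will be asked their normal morning time for inserting lenses and evening time for lens removal". The second is the subject's usual removal time, not the time on a survey day.

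At the end of the study, VAS items cover overall and end-of-day comfort, dryness and quality of vision, alongside the CLDEQ-8 and a lens experience survey.

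**The concern.** The study asks how a lens performs late in a long day, and the observation that bears most directly on this is the state of comfort and vision when the subject stops wearing the lens. The schedule does not capture it. A subject who removes the lenses at 13 h because they are uncomfortable gives ratings at 10 and 12 h and then has no valid answer at 14 or 16 h, because the question is about current comfort in lens wear. That day leaves the late ratings, possibly for the very reason the study is measuring.

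Early removal is foreseeable. Eligibility rests on a yes to wearing lenses over a long day, with no minimum number of hours. Sixteen hours after an 08:00 insertion is midnight, and after 09:00 it is 01:00 (insertion times assumed). Bedtime and discomfort will therefore both end days before the last prompt, and nothing described separates them. At stake are the 14 and 16 h means and the apparent decline from 10 h. With a single arm, there is no comparator in which the distortion might cancel.

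**Working it through.** **What is collected on a survey day, as described**

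| Item | Collected? |
|---|---|
| Insertion time | Yes, each survey morning |
| Comfort and vision, 1-10 | Yes, at 10, 12, 14 and 16 h |
| Comfort and vision at removal | Not described |
| Actual removal time | Not described (usual time only, Visits 1 and 2) |
| Reason for removal | Not described |

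The protocol gives no sample size, SD, expected score or expected share of days ended early, so there is no plan figure to reproduce. Every input below is an assumption.

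**Step 1: the identity.** Let q be the share of subject-days ended before a prompt and d the gap between the mean score on days still in wear and the mean that the ended days would have given. The full mean is (1 - q) × (in-wear mean) + q × (ended-day mean), so the in-wear mean exceeds it by q × d. For example, 0.3 × 2 = 0.6 points. If removal is unrelated to comfort, d = 0 and the bias is 0.

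**Step 2: simulation with removal probabilities that depend on the current rating.** 400,000 days; underlying mean 8.0 at 10 h, falling 0.4 per 2 h; between-subject SD 1.3; within-day SD 1.2; ratings rounded and held to 1-10. The chance of removal before the next prompt is given for ratings of 5 or less / 6-7 / 8 or more. The 10 h mean is 7.89 and the full 16 h mean is 6.78, a decline of 1.11.

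| Dependence on comfort | Removal chance | In wear at 16 h | Raw 16 h mean | Bias | Apparent decline |
|---|---|---|---|---|---|
| None | 20/20/20% | 51% | 6.78 | 0.00 | 1.11 |
| Mild | 30/20/15% | 54% | 6.91 | 0.13 | 0.98 |
| Moderate | 50/25/10% | 52% | 7.12 | 0.34 | 0.77 |
| Strong | 80/30/10% | 45% | 7.31 | 0.54 | 0.58 |

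(Biases were computed before rounding.) In the moderate case the decline is understated by (1.11 - 0.77)/1.11 = 31%.

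**Step 3: simulation with a fixed removal threshold, and what analysis can recover.** 200,000 subject-days; 10 h mean about 7.9; subject SD 1.3, day SD 1.0, residual SD 0.5; decline of 0.2 or 0.3 points per hour; lenses removed before the next prompt whenever the last rating is at or below 4 or 5. Between 76% and 93% of days are still in wear at 16 h. The adjusted estimate regresses each later rating on the earlier ones.

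| Decline, threshold | Full 16 h mean | Raw in-wear mean | Adjusted estimate |
|---|---|---|---|
| 0.2/h, 4 | 6.77 | 6.98 | 6.76 |
| 0.2/h, 5 | 6.79 | 7.29 | 6.75 |
| 0.3/h, 4 | 6.19 | 6.49 | 6.17 |
| 0.3/h, 5 | 6.19 | 6.82 | 6.13 |

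The raw bias is about 0.2 to 0.6 (for example 6.82 - 6.19 = 0.63). After adjustment the error is at most 0.06 in size (6.13 - 6.19 = -0.06). This works because removal here depends only on a rating already recorded.

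**Step 4: removal driven by discomfort that arises between prompts.** The same adjustment then left about 0.2 to 0.7 points of bias, again under assumed values. The score that triggered removal was never recorded, so earlier ratings cannot stand in for it.

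**The case against.** The strongest reply has four parts.

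- **Analysis may deal with it.** A reader might infer that no analysis can recover the late means. Step 3 shows otherwise: where removal follows a recorded low score, a likelihood-type analysis removes nearly all the bias. The protocol does not commit to raw hourly means, and an SAP not seen here may choose better. This stands, but only for that kind of removal. Step 4 is the part that no SAP can repair.
- **Discomfort may not drive removal.** Subjects already wear lenses for long days, Visit 2 checks the fit and allows refitting before the survey days, and the later prompts run towards bedtime. A reader might infer that late scores are certainly inflated; the document does not support that. The direction is conditional. But the data described would not let the sponsor show which case applies.
- **Comfort and vision are rated elsewhere.** The study-end VAS items include end-of-day comfort and vision, so it would be wrong to say that the fixed prompts are the only ratings in the study. They are the only ones on survey days. The VAS items are a single retrospective summary and do not restore ratings for a given day or hour.
- **The forms are not shown, and the target may be comfort while worn.** The wording on survey content is not an exhaustive list, so a lenses-out item could exist; yet every prompt described fires at a fixed hour and none at removal. Comfort among days still in wear is a fair descriptive target for a small exploratory study, provided the report says how many days remain and why the others ended.

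**Conclusion.** The gap in data collection is real. On survey days the protocol describes no score, actual time or reason at lens removal, so the 14 and 16 h ratings describe only days still in wear. If discomfort or poor vision drives some removals, raw hourly means are too high and the decline looks too shallow. The illustrative size is roughly 0.1 to 0.6 points on the 1-10 scale at 16 h, and zero if removal is unrelated to comfort. These figures rest wholly on assumed score distributions and removal rules; nothing in the protocol sets the share of days ended early or their score deficit. Larger values can be had from the identity (40% of days ended with a 3-point gap gives 0.4 × 3 = 1.2), but the document gives no ground for that combination. This is a cheap improvement to the first key endpoint, not an error that invalidates the study.

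**What to change.** On survey days, add one short REDCap survey that the subject opens when the lenses are removed before the 16 h prompt. It holds four items: comfort (1-10), vision (1-10), time of removal, and main reason (discomfort, vision, end of day or schedule, other). It records removal only and changes nothing about when lenses are worn or taken out.

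In the report, give each hourly mean beside the percentage of subject-days still in wear and the percentage ended for discomfort or vision. Also report the end-of-wear score over all survey days.

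The cost is one four-item form, a sentence in the protocol and at most one extra brief response per survey day. No added visits, staff or subjects are needed.

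### Does the Visit 2 dispensing sentence leave existing PRECISION1 Toric wearers with a changed prescription without the right lenses on the survey days?

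*Protocol*

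**What the plan says.** The relevant text is in the protocol's Study Time Points.

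- **Visit 1, existing wearers:** "For any participant who is an existing PRECISION1® Toric wearer, the lenses will be evaluated and the prescription will be refined if necessary". Those who need no change may skip the wait: "Any existing PRECISION1® Toric wearer who does not require any changes in prescription at Visit 1 can immediately advance to Visit 2".
- **Visit 1, everyone else:** "Otherwise, all participants deemed eligible will be dispensed study lenses and Visit 2 will be scheduled". This covers new wearers and also existing wearers whose prescription was just refined. No quantity is given.
- **Visit 2, lens changes:** "If changes to the lens are necessary, those changes will be made and an additional follow up visit will be scheduled". This applies to any participant.
- **Visit 2, supply for the remaining period:** "Subjects who are new to PRECISION1® Contact Lenses will be dispensed additional lenses to wear until Visit 3". No quantity is given here either.
- **Final visit:** "The contact lens follow up visit will occur approximately 1 week (± 5 days) following the follow up visit".

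The Study Overview adds that refitting takes place where needed and that the five survey days are fixed only once Visit 2 has been finally completed. The Background describes the lens as a daily disposable. Evening ratings of comfort and vision on the five days are the first item under Key Endpoints.

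**The concern.** The two visits sort participants by different rules. Visit 1 separates those whose prescription stands from those whose prescription is new or changed. Visit 2 separates those new to the product from those who already wear it. An existing wearer with a changed prescription is inside the Visit 1 dispensing rule and outside the Visit 2 rule.

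Such a wearer's own stock is in the old prescription, and a daily disposable cannot be carried forward from one day to the next. The Visit 2 sentence calls its supply additional, which suggests that the Visit 1 lenses were not expected to reach Visit 3. If nothing more were handed over, the wearer might fall back on old-prescription lenses on the survey days. The evening vision rating would then partly reflect the refraction rather than the lens under study, which would undo the over-refraction done at both visits.

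**Working it through.** The protocol gives no figure for lens supply, so there is none to reproduce. The check traces each kind of participant through the dispensing text and then sizes the supply.

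**Path trace**

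| Participant | Visit 1 | Visit 2 | Position on survey days |
|---|---|---|---|
| New to the product | Study lenses dispensed | Further lenses to Visit 3 | Covered |
| Existing wearer, no change | No study lenses stated | Not named | Presumably own lenses: same product, confirmed prescription |
| Existing wearer, changed at Visit 1 | Study lenses in the refined prescription, quantity not stated | Not named | Depends on the Visit 1 quantity or on staff supplying more |
| Existing wearer, changed at Visit 2 | As in one of the two rows above | Change made, recheck scheduled | New lenses implied, duration not stated |

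**Size of the supply in question**

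Inputs: each visit interval is 1 week ± 5 days (Study Time Points), five survey days fall between Visit 2 and Visit 3, and one pair is used per day (assumption).

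- Stated interval from Visit 2 to Visit 3: 7 − 5 = 2 to 7 + 5 = 12 days.
- Five survey days strictly between the visits need at least 5 + 1 = 6 days, so the workable range is 6 to 12 days, nominally 7. That is 6 to 12 pairs.
- For a Visit 1 supply to reach Visit 3 unaided: nominally 7 + 7 = 14 pairs. The range is 2 + 6 = 8 to 12 + 12 = 24 pairs, or more if an extra follow-up visit is needed.

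**Reading the two affected rows**

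*Changed at Visit 1.* The wearer leaves with lenses in the refined prescription. Whether they last depends on a quantity the protocol leaves open for every participant, new wearers included. The word additional hints that the Visit 1 supply is short, but does not establish it.

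*Changed at Visit 2.* With a daily disposable, making the change and then rechecking it at another visit implies that lenses in the new prescription are handed over. The Study Overview then sets the survey days only after that process is finished. For a wearer to be in the old prescription on a survey day, staff would have to change the lens, confirm the new one and send the participant away without it. The row is also narrow. For an existing wearer who moved straight from Visit 1 to Visit 2, a change would reverse an assessment just made. Most of the other existing wearers in this row were already changed at Visit 1.

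**Bound on the effect**

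Entry carries its own limit: "Subjects must have 20/25 or better distance visual acuity with current lenses". Even a wearer who fell back on old lenses would be in a correction that met this standard at enrolment. The protocol does not give the number of existing wearers, the share whose prescription changes or the effect on a 1–10 rating, so no bias can be calculated.

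**The case for a change.** The strongest case for acting is that the protocol itself foresees these wearers, since it says their prescription may be refined, and then omits them from the only supply described as lasting to Visit 3. Dispensing is protocol content, not something left to a statistical analysis plan. The ratings at risk are the first-listed key endpoint, and the repair would cost one sentence and about 7 pairs of lenses per wearer supplied.

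Part of this stands. The two sentences do not line up, and no other text states a supply to Visit 3 for this group. The remark about own stock does not help a wearer whose prescription has changed.

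The step from omission to harm does not stand. A sentence saying that one group will receive lenses does not say that others will not, so reading it as an allocation of zero pairs is an inference. No two statements conflict and no number is wrong. Low cost alone does not justify a change when no gain can be shown, and here both the number affected and the effect may be nil.

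**Conclusion.** No change to the plan is called for. This is an incompletely worded logistics sentence that site staff can be expected to fill sensibly, because the purpose of Visits 1 and 2 is to put every participant into a confirmed fit before the survey days.

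What remains open is mainly the existing wearer changed at Visit 1, for whom nominally 7 pairs (6 to 12) after Visit 2 are not explicitly assigned. That figure assumes one pair per day and five survey days strictly between the two visits. The conclusion also assumes that staff who refit a participant will supply the refitted lens, and that existing wearers with no change use their own lenses of the same product, which is harmless to the ratings. No sample size, endpoint definition, analysis or interpretation turns on the point.

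### At the final visit the VAS key endpoint and the CLDEQ-8 are completed after acuity testing and the eye assessment; asking them first would remove an avoidable, minor source of bias

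*Protocol*

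**What the plan says.** The Protocol's Final visit paragraph (Study Time Points) lists the clinical procedures first: "Subjects will have visual acuity, an assessment of ocular health". The sentence that follows is "Subjects will then complete surveys about their lens wear experience".

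The content of those surveys is given a few lines later: "End of study surveys will include a lens experience survey, the CLDEQ-8 survey, and VAS scales assessing" overall and end-of-day quality of vision, comfort and dryness, which makes six items. The Study Overview places the same instruments at this visit: "Participants will return for a final follow-up visit including a VAS survey and the CLDEQ8 survey of their lens wear experience".

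Key Endpoints has two entries. One is the 1 to 10 rating of comfort and vision on five evenings. The other is "Visual Analog Scale survey of lens wear symptoms (comfort, dryness, vision) at study end". The CLDEQ-8 is not listed there.

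On the design, the Study Overview says: "This open-label study is of current soft contact lens wearers who wear their contact lenses for longer than a typical workday". One lens type is fitted, and no comparator is described.

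**The concern.** The VAS and CLDEQ-8 are self-reports about the period of wear that has just ended. Ideally they are taken before anything at the visit can alter the subject's view of that period. In the stated order, a subject rates quality of vision soon after reading an acuity chart, and rates comfort and dryness soon after an eye assessment. Fresh information about acuity or eye health could enter the answers.

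The design offers no protection. Subjects know which lens they wear, and no control group is described in which a shared examination effect would cancel. The Protocol also specifies no VAS before the final visit, so no stated change score would remove it. What is at stake is the reported level of one of the two key endpoints, and the only one that covers dryness.

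**Working it through.** No formula applies. The Protocol gives no sample size, standard deviation, error rate or effect size; under Statistical Analysis and Power Calculation it says only "This small sample size was chosen for convenience as this study as enrollment for evening participation may be difficult". The check is a reading of the sections against each other.

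1. **Is the order fixed?** Yes. The word *then* in "Subjects will then complete surveys about their lens wear experience" places the surveys after the acuity test and the ocular health assessment named in the sentence before it.

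2. **Are these the endpoint surveys?** Yes. The list of end-of-study surveys includes the VAS, the Study Overview puts the VAS and CLDEQ-8 at the final visit, and Key Endpoints names the study-end VAS.

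3. **Does any other section change the order or shield the ratings?** No. No section puts the surveys first, and none says that acuity or examination findings are held back until the surveys are done.

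4. **Which measures are exposed?** Three domains (vision, comfort, dryness) times two time frames (overall, end of day) gives six VAS items. The CLDEQ-8 and the lens experience survey are exposed as well. The evening ratings are not: they are answered on the subject's own device between Visits 2 and 3. They cover comfort and vision, the domains of four of the six VAS items. The two dryness items have no evening counterpart.

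5. **Would a shift survive analysis?** A shift in the same direction for most subjects would remain in the mean, since there is no comparator to subtract. Shifts of mixed sign would act mainly as noise, which averaging over subjects reduces. Since every subject follows the same order, no later analysis could separate an examination effect from the lens experience.

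6. **How large could it be?** This cannot be derived. The Protocol does not describe the assessment, who performs it, what subjects are told, or how long afterwards the surveys are filled in.

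**The case against.** The strongest case against the point is that the sequence is a fact but a material bias is not shown.

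- **Recall.** All six VAS items ask for overall or end-of-day experience, not for how the eye feels in the clinic. This stands as a limit on momentary discomfort. It limits feedback about vision or eye health less.
- **Familiar testing.** Acuity is also measured at Visits 1 and 2, with over-refraction and refitting where needed, and entry requires 20/25 or better. One more chart reading may tell the subject little. This stands as a reason to expect a small effect, not as a reason for the order.
- **A parallel measure.** The evening ratings cover comfort and vision close to the time of wear and are untouched. This stands, except for dryness.
- **A larger problem remains.** Open-label expectation without a comparator persists under either order. True, but that does not justify leaving in a source that can be removed.
- **Exploratory purpose.** The study sets out to explore performance and states no threshold or test that a small shift would overturn. This stands and lowers the severity.

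A reader might go further and infer that the VAS scores are biased by some definite amount, that confidence intervals would lose coverage to a calculable degree, that the staff who fitted the lens also examine the subject and comment on the result, or that the lenses have been removed before the ratings. The Protocol supports none of these. It gives no scale length, variance or shift from which to calculate, and it is silent on the examiner, on feedback and on lens removal. Nor would every shift escape averaging; only one with a common direction would.

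**Conclusion.** The point holds as a minor one. The order is explicit, it affects one of two key endpoints together with the CLDEQ-8, and nothing else in the Protocol offsets it. The conclusion that ratings *could* be influenced rests on the ratings being subjective, the study being open-label and no comparator being described; all three can be read from the text. That they *are* influenced, by how much and in which direction, cannot be established from the Protocol.

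The study is not invalidated and the evening ratings are unaffected. The order of visit procedures is protocol content, and this Protocol states it, so the point is not one that a statistical analysis plan would be expected to settle.

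**What to change.** Change the Final visit paragraph so that the self-reports come first. For example: *On arrival, before visual acuity, the ocular health assessment or any discussion of findings, subjects complete the VAS scales, the CLDEQ-8 and the lens experience survey. Visual acuity and the ocular health assessment follow.*

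Keep whatever mode of completion the study already uses; the Protocol fixes none for these surveys, and the point does not depend on it.

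The cost is a reordering within one paragraph. It adds no procedure, visit time or subjects, and no clinical procedure changes in content. It must be made before the first final visit, so that all subjects follow the same order.
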